3.4 Statistical methods

Statistical analyses will be performed using two-sided tests, without adjustment for multiplicity. All p-values will be interpreted descriptively.

Data will be summarized by treatment group (and by visit when applicable), with respect to demographic and baseline characteristics, efficacy variables, and safety variables.

Summary statistics will include the mean, number of non-missing cases (n), standard deviation, median, minimum, and maximum values for continuous variables, and frequencies and percentages for categorical variables.

Categorical efficacy variables will be analyzed using the Cochran-Mantel-Haenszel (CMH) test with stratification by (pooled) analysis center and the Fisher's exact test in case of analyses without stratification (mainly for safety assessment).

Selected scores will be analyzed using an analysis of covariance (ANCOVA) model, with treatment group and (pooled) analysis center as factors and baseline outcome as covariate.

Time to event data will be analyzed using the Kaplan-Meier method, and treatment group differences will be tested by the log-rank test.

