3.4.5 Compliance

The % treatment compliance will be determined as the number of performed treatment applications in relation to the planned applications within the individual subjects treatment phase:

- total number of applications =
planned applications – # missed applications + # overdose applications
- % treatment compliance =
100 * total number of applications / # planned applications

The % dosing compliance will be determined as the number of dosed capsules in relation to the number of planned capsules within the individual subjects treatment phase:

- total number of dosed capsules =
$$6 * \# \text{ planned applications} - \# \text{ missed capsules} + \# \text{ overdose capsules}$$
- % dosing compliance =
$$100 * \text{total number of dosed capsules} / (6 * \# \text{ planned applications})$$

The % treatment compliance and % dosing compliance will be summarized by descriptive statistics and frequency counts will be given for sufficient ($\geq 80\%$) and insufficient ($< 80\%$) compliance.

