The following subgroups, based on baseline parameter, will be evaluated with respect to the primary efficacy variables PASI and PGA for each post-baseline visit within the FAS:

Table 4 Subgroups

Center:	• Analysis (pooled) centers		
Age:	• 18 to 40	• >40	
Sex:	• Male	• Female	
BMI:	• ≤ 24.9 (normal)	• 25.0 - 29.9 (pre-obesity)	• ≥ 30.0 (obesity)
Years of psoriasis:	• 1 to 10	• >10	
Smoking	• Current	• Never or former	
Cigarette smoking:	• <1 to 10	• >10	
PGA:	• 3 to 4	• 5 to 6	
PASI:	• ≤ 15	• > 15	
CRP:	• <10 mg/dl	• ≥ 10 mg/dl	

The change in PASI and PGA will be evaluated utilizing following analyses:

- mean change from baseline in PASI by ANCOVA model
- location shift in change from baseline in PGA by Wilcoxon rank sum test and Hodges-Lehmann Estimation

If applicable, the analyses will be stratified by country.

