3.4.7.5 Extent of exposure to study drug

The overall extent of exposure to study drug will be summarized by

- total number of applications =
planned applications – # missed applications + # overdose applications
- total number of dosed capsules =
6 * # planned applications – # missed capsules + # overdose capsules
- average number of capsules per application =
total number of dosed capsules / total number of applications

- duration of the treatment (days of treatment) =
duration from first dose to last dose in days, start and end day included.
- average number of capsules per day =
total number of dosed capsules / days of treatment
- % exposure =
 $100 * \text{total number of dosed capsules} / (84 * 2 * 6)$

For each treatment descriptive statistics will be given. Duration of treatment will additionally be presented by a frequency table for categorized numbers of days (less than 26 days, 26 to 53 days, 54 to 83 days, 84 days and more) and % exposure will be presented by exposure of less than 80% and 80% and more. .

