Exception: Treatment related discontinuations, i.e. discontinuations due to adverse events at least possibly related to IMP.

Source data: <DATASET> <DATE>

Program: <SAS PROGRAM> <DATE>

Table 14.2.1: Subject demographics (SES)
(Part 1 of 1)

	MP1032 300 mg bid (N = XX)	MP1032 150 mg bid (N = XX)	Placebo bid (N = XX)	Total (N = XX)
Age [years]				
N	XX	XX	XX	XX
Mean ± SD	XX.X ± XX.X	XX.X ± XX.X	XX.X ± XX.X	XX.X ± XX.X
Median	XX X	XX X	XX X	XX X
Min , max	XX , XX	XX , XX	XX , XX	XX , XX
Sex				
N	XX	XX	XX	XX
Male	XX (XXX.X%)	XX (XXX.X%)	XX (XXX.X%)	XX (XXX.X%)
Female	XX (XXX.X%)	XX (XXX.X%)	XX (XXX.X%)	XX (XXX.X%)
Race				
N	XX	XX	XX	XX
American Indian or Alaska Native	XX (XXX.X%)	XX (XXX.X%)	XX (XXX.X%)	XX (XXX.X%)
Asian	XX (XXX.X%)	XX (XXX.X%)	XX (XXX.X%)	XX (XXX.X%)
Black or African American	XX (XXX.X%)	XX (XXX.X%)	XX (XXX.X%)	XX (XXX.X%)
Multiple Races	XX (XXX.X%)	XX (XXX.X%)	XX (XXX.X%)	XX (XXX.X%)
Native Hawaiian or Other Pacific Islander	XX (XXX.X%)	XX (XXX.X%)	XX (XXX.X%)	XX (XXX.X%)
White	XX (XXX.X%)	XX (XXX.X%)	XX (XXX.X%)	XX (XXX.X%)
Other	XX (XXX.X%)	XX (XXX.X%)	XX (XXX.X%)	XX (XXX.X%)

Source data: <DATASET> <DATE>
Program: <SAS PROGRAM> <DATE>

Table 14.2.2: Subject demographics (FAS)
Analog to Table 14.2.1 for FAS

Table 14.2.3: Subject demographics (VCS)
Analog to Table 14.2.1 for VCS

Table 14.2.4: Subject demographics (PKS)
Analog to Table 14.2.1 for PKS

Table 14.2.5: Subject baseline characteristics (SES)
(Part 1 of 1)

	MP1032 300 mg bid (N = XX)	MP1032 150 mg bid (N = XX)	Placebo bid (N = XX)	Total (N = XX)
Height [cm]				
N	XX	XX	XX	XX
Mean ± SD	XX.X ± XX.X	XX.X ± XX.X	XX.X ± XX.X	XX.X ± XX.X
Median	XX X	XX X	XX X	XX X
Min , max	XX , XX	XX , XX	XX , XX	XX , XX
Weight [kg]				
N	XX	XX	XX	XX
Mean ± SD	XX.X ± XX.X	XX.X ± XX.X	XX.X ± XX.X	XX.X ± XX.X
Median	XX.X	XX.X	XX.X	XX.X
Min , max	XX , XX	XX , XX	XX , XX	XX , XX
BMI [kg/m ²]				
N	XX	XX	XX	XX
Mean ± SD	XX.X ± XX.X	XX.X ± XX.X	XX.X ± XX.X	XX.X ± XX.X
Median	XX.X	XX.X	XX.X	XX.X
Min , max	XX , XX	XX , XX	XX , XX	XX , XX

Source data: <DATASET> <DATE>
Program: <SAS PROGRAM> <DATE>

Table 14.2.6: Subject baseline characteristics (FAS)
Analog to Table 14.2.5 for FAS

Table 14.2.7: Subject baseline characteristics (VCS)
Analog to Table 14.2.5 for VCS

Table 14.2.8: Subject baseline characteristics (PKS)
Analog to Table 14.2.5 for PKS

Table 14.2.9: Baseline psoriasis (SES)
(Part 1 of 1)

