Table 14.4.5: PASI – Subgroup: Years of psoriasis – ANCOVA for change from baseline – LOCF (FAS)
Analog to Table 14.3.7 for Subgroups: Years of psoriasis: 1 to 10; >10.

Table 14.4.6: PASI – Subgroup: Smoking – ANCOVA for change from baseline – LOCF (FAS)
Analog to Table 14.3.7 for Subgroups: Smoking: Current; Never or former.

Table 14.4.7: PASI – Subgroup: Cigarette smoking – ANCOVA for change from baseline – LOCF (FAS)
Analog to Table 14.3.7 for Subgroups: Cigarette smoking: <1 to 10; >10.

Table 14.4.8: PASI – Subgroup: PGA – ANCOVA for change from baseline – LOCF (FAS)
Analog to Table 14.3.7 for Subgroups: PGA: 3 to 4; 5 to 6.

Table 14.4.9: PASI – Subgroup: PASI – ANCOVA for change from baseline – LOCF (FAS)
Analog to Table 14.3.7 for Subgroups: PASI: ≤ 15 ; > 15.

Table 14.4.10: PASI – Subgroup: CRP – ANCOVA for change from baseline – LOCF (FAS)
Analog to Table 14.3.7 for Subgroups: CRP: <10 mg/dl; ≥ 10 mg/dl.

Table 14.4.11: PASI – Subgroup: % Exposure – ANCOVA for change from baseline – LOCF (FAS)
Analog to Table 14.3.7 for Subgroups: % Exposure: < 80%; $\geq 80\%$.

Table 14.4.12: PGA – Subgroup: Analysis center – Location shift in change from baseline – LOCF (FAS)
(Part 1 of 2)

PGA changes from baseline Analysis center (pooled): 01	MP1032 300 mg bid (N = XX)	MP1032 150 mg bid (N = XX)	Placebo bid (N = XX)
Week 4			
N	XX	XX	XX
Mean ± SD	X.X ± X.X	X.X ± X.X	X.X ± X.X
Median	X.X	X.X	X.X
Min , max	X , X	X , X	X , X
Comparison vs Placebo			
Estimate ± SE ¹	X.X ± X.XX	X.X ± X.XX	--
95%-CI ¹	X.X , X.X	X.X , X.X	--
p-value ²	X.XXX	X.XXX	--
Week 8			
N	XX	XX	XX
Mean ± SD	X.X ± X.X	X.X ± X.X	X.X ± X.X
Median	X.X	X.X	X.X
Min , max	X , X	X , X	X , X
Comparison vs Placebo			
Estimate ± SE ¹	X.X ± X.XX	X.X ± X.XX	--
95%-CI ¹	X.X , X.X	X.X , X.X	--
p-value ²	X.XXX	X.XXX	--
Week 12 / EoT			
N	XX	XX	XX
Mean ± SD	X.X ± X.X	X.X ± X.X	X.X ± X.X
Median	X.X	X.X	X.X
Min , max	X , X	X , X	X , X
Comparison vs Placebo			
Estimate ± SE ¹	X.X ± X.XX	X.X ± X.XX	--
95%-CI ¹	X.X , X.X	X.X , X.X	--
p-value ²	X.XXX	X.XXX	--

¹ Estimates and confidence interval by Hodges-Lehmann estimation using location shift.

² Wilcoxon rank sum test.

Source data: <DATASET> <DATE>
Program: <SAS PROGRAM> <DATE>

Table 14.4.12: PGA – Subgroup: Analysis center – Location shift in change from baseline – LOCF (FAS)
(Part 2 of 2)

PGA changes from baseline Analysis center (pooled): 01	MP1032 300 mg bid (N = XX)	MP1032 150 mg bid (N = XX)	Placebo bid (N = XX)
Week 16 / Follow up			
N	XX	XX	XX

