Mean ± SD	X.X ± X.X	X.X ± X.X	X.X ± X.X
Median	X.X	X.X	X.X
Min , max	X , X	X , X	X , X
Comparison vs Placebo			
Estimate ± SE ¹	X.X ± X.XX	X.X ± X.XX	--
95%-CI ¹	X.X , X.X	X.X , X.X	--
p-value ²	X.XXX	X.XXX	--

¹ Estimates and confidence interval by Hodges-Lehmann estimation using location shift.

² Wilcoxon rank sum test.

Source data: <DATASET> <DATE>

Program: <SAS PROGRAM> <DATE>

Table 14.4.13: PGA – Subgroup: Age – Location shift in change from baseline – LOCF (FAS)
Analog to Table 14.3.7 for Subgroups: Age: 18 to 40; >40.

Table 14.4.14: PGA – Subgroup: Sex – Location shift in change from baseline – LOCF (FAS)
Analog to Table 14.3.7 for Subgroups: Sex: Male; Female.

Table 14.4.15: PGA – Subgroup: BMI – Location shift in change from baseline – LOCF (FAS)
Analog to Table 14.3.7 for Subgroups: BMI: Normal (≤ 24.9); Pre-obesity (25.0 - 29.9); Obesity (≥ 30.0).

Table 14.4.16: PGA – Subgroup: Years of psoriasis – Location shift in change from baseline – LOCF (FAS)
Analog to Table 14.3.7 for Subgroups: Years of psoriasis: 1 to 10; >10.

Table 14.4.17: PGA – Subgroup: Smoking – Location shift in change from baseline – LOCF (FAS)
Analog to Table 14.3.7 for Subgroups: Smoking: Current; Never or former.

Table 14.4.18: PGA – Subgroup: Cigarette smoking – Location shift in change from baseline – LOCF (FAS)
Analog to Table 14.3.7 for Subgroups: Cigarette smoking: <1 to 10; >10.

Table 14.4.19: PGA – Subgroup: PGA – Location shift in change from baseline – LOCF (FAS)
Analog to Table 14.3.7 for Subgroups: PGA: 3 to 4; 5 to 6.

Table 14.4.20: PGA – Subgroup: PASI – Location shift in change from baseline – LOCF (FAS)
Analog to Table 14.3.7 for Subgroups: PASI: ≤ 15 ; > 15.

Table 14.4.21: PGA – Subgroup: CRP – Location shift in change from baseline – LOCF (FAS)
Analog to Table 14.3.7 for Subgroups: CRP: <10 mg/dl; ≥ 10 mg/dl.

Table 14.4.22: PGA – Subgroup: % Exposure – Location shift in change from baseline – LOCF (FAS)
Analog to Table 14.3.7 for Subgroups: % Exposure: < 80%; $\geq 80\%$.

Table 14.4.23: Extent of exposure (SES)
(Part 1 of 1)

	MP1032 300 mg bid (N = XX)	MP1032 150 mg bid (N = XX)	Placebo bid (N = XX)
Total number of applications¹			
N	XXX	XXX	XXX
Mean ± SD	XX.X ± XX.X	XX.X ± XX.X	XX.X ± XX.X
Median	XX.X	XX.X	XX.X
Min , max	XX , XX	XX , XX	XX , XX
Total number of dosed capsules²			
N	XX	XX	XX
Mean ± SD	XX.X ± XX.X	XX.X ± XX.X	XX.X ± XX.X
Median	XX.X	XX.X	XX.X
Min , max	XX , XX	XX , XX	XX , XX

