Treatment duration³			
N	XX	XX	XX
Mean ± SD	XX.X ± XX.X	XX.X ± XX.X	XX.X ± XX.X
Median	XX.X	XX.X	XX.X
Min , max	XX , XX	XX , XX	XX , XX
Less than 28 days	XX (XXX.X%)	XX (XXX.X%)	XX (XXX.X%)
29 to 56 days	XX (XXX.X%)	XX (XXX.X%)	XX (XXX.X%)
57 to 84 days	XX (XXX.X%)	XX (XXX.X%)	XX (XXX.X%)
More than 84 days	XX (XXX.X%)	XX (XXX.X%)	XX (XXX.X%)
Average number of capsules per application⁴			
N	XX	XX	XX
Mean ± SD	XX.X ± XX.X	XX.X ± XX.X	XX.X ± XX.X
Median	XX.X	XX.X	XX.X
Min , max	XX.X , XX.X	XX.X , XX.X	XX.X , XX.X
Average number of capsules per day⁵			
N	XX	XX	XX
Mean ± SD	XX.X ± XX.X	XX.X ± XX.X	XX.X ± XX.X
Median	XX.X	XX.X	XX.X
Min , max	XX.X , XX.X	XX.X , XX.X	XX.X , XX.X
% Exposure⁶			
N	XX	XX	XX
Mean ± SD	XXX.X ± XXX.X	XXX.X ± XXX.X	XXX.X ± XXX.X
Median	XXX.X	XXX.X	XXX.X
Min , max	XXX , XXX	XXX , XXX	XXX , XXX
Insufficient (< 80%)	XX (XXX.X%)	XX (XXX.X%)	XX (XXX.X%)
Sufficient (≥ 80%)	XX (XXX.X%)	XX (XXX.X%)	XX (XXX.X%)

¹ Total number of applications = # planned applications – # missed applications +# overdose applications

² Total number of dosed capsules = 6 * # planned applications – # missed capsules” + # overdose capsules

³ Treatment duration = date of last dose – date of first dose + 1.

⁴ Average number of capsules per application = # dosed capsules / # applications

⁵ Average number of capsules per day = # dosed capsules / days of treatment

⁶ % Exposure = 100 * # dosed capsules / (84 * 2 * 6)

Table 14.5.1: Overview on adverse events (SES)
(Part 1 of 1)

Adverse events Count¹ / Incidence² (Incidence rate%³)	MP1032 300 mg bid (N = XX)	MP1032 150 mg bid (N = XX)	Placebo bid (N = XX)
TEAEs ⁴	XXX / XX (XXX X%)	XXX / XX (XXX X%)	XXX / XX (XXX X%)
TEAEs by intensity ⁵			
Severe	XXX / XX (XXX.X%)	XXX / XX (XXX.X%)	XXX / XX (XXX.X%)
Moderate	XXX / XX (XXX.X%)	XXX / XX (XXX.X%)	XXX / XX (XXX.X%)
Mild	XXX / XX (XXX.X%)	XXX / XX (XXX.X%)	XXX / XX (XXX.X%)
TEAEs by relation to the IMP ⁵			
Certain	XXX / XX (XXX.X%)	XXX / XX (XXX.X%)	XXX / XX (XXX.X%)
Probable	XXX / XX (XXX.X%)	XXX / XX (XXX.X%)	XXX / XX (XXX.X%)
Possible	XXX / XX (XXX.X%)	XXX / XX (XXX.X%)	XXX / XX (XXX.X%)
Unlikely	XXX / XX (XXX.X%)	XXX / XX (XXX.X%)	XXX / XX (XXX.X%)
Not related	XXX / XX (XXX.X%)	XXX / XX (XXX.X%)	XXX / XX (XXX.X%)
Serious TEAEs	XXX / XX (XXX.X%)	XXX / XX (XXX.X%)	XXX / XX (XXX.X%)
TEAEs leading to study discontinuation	XXX / XX (XXX.X%)	XXX / XX (XXX.X%)	XXX / XX (XXX.X%)

¹ Count of AEs reported

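### Two exploratory SAP shells compare drug with placebo within levels of % Exposure, a post-randomisation variable missing from the SAP's subgroup list; the CRP cut-off unit also needs confirming

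*SAP*

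**What the plan says.** **Subgroup scope.** SAP 3.4.6.2 opens its subgroup list with "The following subgroups, based on baseline parameter, will be evaluated". Table 4 then names center, age, sex, BMI, years of psoriasis, smoking, cigarettes, PGA, PASI and CRP. Exposure is not there.

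**Exposure in the SAP text.** In 3.4.7.5 the 80% split is only a way of summarising exposure: "exposure will be presented by exposure of less than 80% and 80% and more". The definition, repeated under Table 14.4.23, is "Exposure = 100 * # dosed capsules / (84 * 2 * 6" with the bracket closed.

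**Exposure in the shells.** Table 14.4.11 (PASI, ANCOVA) is specified as "Analog to Table 14.3.7 for Subgroups: % Exposure: < 80" per cent, against 80% and above. The PGA counterpart is "Table 14.4.22: PGA – Subgroup: % Exposure – Location shift in change from baseline – LOCF (FAS").

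**Another use of 80%.** The footnotes to Table 14.1.3 define Week 12 completion as a PASI visit on study days 80 to 91 together with at least 80% of planned exposure.

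**CRP.** Table 4 and shells 14.4.10 and 14.4.21 cut at 10 mg/dl. Table 14.6.21 reports CRP in mg/L.

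**Other splits.** Years of psoriasis are grouped as 1 to 10 and over 10; baseline PGA as 3 to 4 and 5 to 6.

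**The concern.** A subgroup comparison with placebo keeps the protection of randomisation only if subgroup membership is fixed before treatment starts. % Exposure depends on how long and how faithfully the patient took the capsules. That can depend on tolerability and on response, and both may differ by arm. A difference from placebo within the lower or upper exposure level therefore cannot be read as a drug effect, and the likely misreading is that the drug works in patients who take enough of it. Missing scores up to Day 84 are also carried forward (SAP 3.5.1), so many Week 12 values in the lower level will be earlier ones.

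For CRP, two programmers could produce different subgroups from the same plan: one by applying the cut-off as written, the other by applying the number 10 to values held in mg/L.

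**Working it through.** **Inputs.** Six capsules twice daily for 84 days (protocol 5.4.1); the exposure formula (SAP 3.4.7.5); templates 14.3.7 and 14.4.12, each printing results against placebo at Weeks 4, 8, 12 and 16; two active doses. Two doses are counted on Day 1 and no overdose capsules are assumed.

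**Denominator.** 84 × 2 × 6 = 1008 capsules. 80% of 1008 = 806.4.

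**Highest possible exposure at 12 capsules per day:**

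| Day | Capsules | % Exposure |
|---|---|---|
| 28 (nominal Week 4) | 336 | 33.3 |
| 56 (nominal Week 8) | 672 | 66.7 |
| 58 (end of Week 8 window) | 696 | 69.0 |
| 67 | 804 | 79.8 |
| 68 | 816 | 81.0 |

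If only one dose is taken on Day 1, Day 68 gives 816 − 6 = 810 capsules, or 80.4%, so the threshold day does not move. To reach 806.4 by Day 58 a patient would need more than 110 overdose capsules (806.4 − 696 = 110.4).

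At Week 4 and Week 8, then, no patient has yet qualified for the upper level. Who ends up in it is decided by what happens afterwards. Anyone who stops by Week 8 falls in the lower level.

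**Number of comparisons.** 2 outcomes × 2 levels × 4 visits × 2 doses = 32. At Weeks 4 and 8 only: 2 × 2 × 2 × 2 = 16.

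**Template reference.** Shell 14.4.22 is titled as a location shift but cites the ANCOVA template 14.3.7. The location-shift layout is in 14.4.12. Both print the placebo contrast, so the point does not depend on which is meant. The same mismatch runs through all of 14.4.13 to 14.4.22.

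**CRP.** 10 mg/dl × 10 dl/L = 100 mg/L. The cut-off as written is ten times the number 10 read in the lab-table unit.

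**Range gaps.** Inclusion criterion 2c requires at least 6 months of stable disease, and SAP 3.4.1 keeps years of psoriasis to one decimal. A duration of 0.5 to 0.9 years is therefore possible and has no cell. Imputing missing onset days and months to the earliest date (SAP 3.5.1) lengthens recorded duration; this narrows the gap without closing it. No entry criterion sets a minimum PGA, so a baseline PGA of 2 or lower is formally possible and also has no cell.

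**The case against.** The strongest reply is that nothing rests on these tables. The trial postulates no hypotheses, and SAP 3.4 states: "All p-values will be interpreted descriptively". The shells are disclosed in advance, and the appendix already uses an 80% exposure rule for Week 12 completion, so the split is less isolated than the SAP text suggests. The SAP also prints placebo comparisons in another set selected after randomisation, the VCS (Tables 14.3.10 and 14.3.13).

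Most of this stands and it limits the severity. It does not remove the defect. Labelling p-values descriptive deals with confirmatory claims; it does not make the arms within an exposure level comparable. The completion rule shows that the appendix counts low exposure as discontinuation, which is a reason for more caution.

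The VCS is declared in the text as a sensitivity set and is built differently. Dosing compliance is taken "in relation to the number of planned capsules within the individual subjects treatment phase", and the footnote to Table 14.1.4 adds "Exception: Treatment related discontinuations, i.e. discontinuations due to adverse events at least possibly related to IMP". A fully adherent patient who stops on Day 56 has 100% dosing compliance but 66.7% exposure, although the requirement for completed Day 84 assessments would usually exclude that patient from the VCS anyway. The VCS is neither an equivalent of the exposure split nor a justification for it.

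A reader might also suppose that the comparison is safe if patients stop for the same reasons in every arm. That is not generally so. As an illustration on assumptions outside the documents, take normally distributed response, a true difference of 0.5 SD, and one response threshold for stopping that removes the worst 20% of placebo patients. The remaining patients then differ by about 0.33 SD.

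**Conclusion.** The point holds as a minor-to-moderate one, confined to exploratory tables. The SAP text and the shells disagree on whether % Exposure is a subgroup variable, and 32 placebo comparisons would be printed within levels of a post-randomisation variable. Sixteen of them concern visits at which, without overdose capsules, no patient could yet have reached the threshold. The primary CMH analyses and the sample size are not affected.

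Three stronger readings are not supported:

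- **That the tables will favour the drug, or will be biased by some stated amount.** The documents give no stopping rates or reasons by arm, so neither direction nor size can be derived.
- **That the CRP cut-off is a misprint for 10 mg/L.** The value 10 mg/dl is well defined and is used consistently in Table 4 and both shells. The documents show a unit mismatch with the lab table but not which value was intended. They give no CRP distribution, so the size of the upper stratum is unknown. This is a query to the sponsor.
- **That the range gaps will lose a meaningful number of patients.** Criterion 2c concerns stable disease, so it is only a lower bound on time since onset. A PGA of 2 is unlikely in patients with investigator-diagnosed moderate-to-severe disease, PASI of at least 10 and BSA above 10%. The number affected is unknown and probably small.

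**What to change.** 1. **Exposure.** Remove the placebo estimate, confidence interval and p-value from Tables 14.4.11 and 14.4.22, keep them as descriptive summaries by arm, and declare % Exposure in SAP 3.4.6.2 as a post-randomisation, non-randomised split. Alternatively, delete both tables.
2. **CRP query.** The sponsor confirms the intended cut-off before unblinding and states it in mg/L in Table 4 and in shells 14.4.10 and 14.4.21.
3. **Template references.** Those of shells 14.4.13 to 14.4.22 that are kept should cite 14.4.12.
4. **Footnote-level tidying.** Use ≤10 / >10 years and PGA ≤4 / ≥5 in Table 4 and shells 14.4.5, 14.4.8, 14.4.16 and 14.4.19.

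The cost is SAP and shell wording before unblinding. Keeping the exposure tables as summaries gives up only the placebo contrasts; deleting them gives up 32 exploratory comparisons that were not randomised comparisons. Sample size, endpoints and data collection do not change.
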